3.2.1. INCLUSION CRITERIA

Each potential subject must satisfy all of the following criteria to be enrolled in the study:

1. Adult male or female ≥ 18 years of age at the time of signing the informed consent form (ICF)
2. Clinical diagnosis of acquired TTP (initial or recurrent), which includes thrombocytopenia and microscopic evidence of red blood cell fragmentation (e.g. schistocytes)
3. Requires initiation of daily PE treatment and has received 1 PE treatment^{§§} prior to randomization
4. Female subjects of childbearing potential (excluding postmenopausal women, sterilized, ovariectomized and hysterectomized women) must have a negative pregnancy test and must agree to use a generally accepted adequate contraceptive method from screening until at least 2 months after last dosing
5. Subjects have provided informed consent prior to initiation of any study specific activity/procedure. In case the subject is unconscious or if their ability to give (written) informed consent is compromised due to the neurological impairment or severity of TTP symptoms, a subject's legal acceptable representative or independent physician (as per local law and Ethics Committee [EC]/Institutional Review Board [IRB] approval) has provided informed consent prior to any study specific activity/procedure.

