3.4.11. APPROPRIATENESS AND TIMING OF MEASUREMENTS

The assessments which will be made in this study are standard and generally recognized as reliable, accurate, and relevant.

The timing of all assessments is detailed in the [Schedules of Assessments](#).

During the daily PE period, samples for PK, PD, disease-related markers and safety will be obtained on the day itself and prior to PE (for Day 1, i.e., prior to the i.v. dose administration).

Following guidance with regard to timing of assessments planned at a single visit should be followed:

- 1) ECG and vital signs should be assessed prior to blood sampling, and
- 2) Assessments should be done prior to start of PE (and on Day 1, prior to the i.v. dose administration), and
- 3) s.c. study drug should be dosed after all other assessments have been performed (and during the daily PE period, s.c. study drug should be dosed after end of the day's PE).

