9 IMMUNOGENICITY ANALYSIS

9.1 Available data

9.1.1 ADA and mADA analysis

9.1.1.1 ADA analysis

Immunogenicity samples will be evaluated in the bridging ADA assay. All samples scoring positive in the ADA assay will be titrated. The $\log_{10}(\text{titer})$ will be reported. The titer represents the last dilution factor of the sample's titration series still scoring positive in the ADA assay. Samples scoring negative in the ADA assay are not titrated and the respective $\log_{10}(\text{titer})$ is reported as $<\log_{10}(\text{Minimal required dilution [MRD]})$ with MRD=96, i.e. $\log_{10}(\text{titer}) < 1.98$. The latter are not included in descriptive statistics on titers.

Subjects will be classified as follows based on the ADA assay results:

- ADA negative: no positive ADA samples at any of the sampling time points
- ADA positive: positive ADA samples at one or more sampling time points
- Inconclusive: no positive ADA samples and drug is present at levels higher than the drug tolerance characteristics of the assay
- Missing: relevant samples are missing

No statement will be made on pre-existing antibody (pre-Ab) positivity pre-dose due the plasma exchange (PE) procedure. During PE (i) pre-Ab present in donor plasma can be transferred to the patient and/or (ii) pre-Ab might be diluted during PE treatment. Since all the patients will be treated with one PE before the first caplacizumab administration, no ADA pre-PE sample will be available to determine the pre-Ab status of the patient.

9.1.1.2 mADA

All positive ADA samples will be further evaluated using the modified ADA (mADA) assay. This assay employs a modified caplacizumab molecule as detection reagent in the bridging format, i.e. caplacizumab-Ala variant. The modification constitutes of a single alanine extension at the C-terminus of caplacizumab. The mADA assay allows detection of drug-induced treatment-emergent (TE) ADA, whereas pre-Ab are not detected. In other words, drug-induced TE ADA will score positive in the mADA assay. Only TE ADA responses with a restricted repertoire, directed against the C-terminal part of the Nanobody (i.e. C-terminal part of the last Nanobody domain), which might be shielded by the presence of the additional alanine on the detector reagent might be left undetected using this mADA assay. All samples scoring positive in the mADA assay will be titrated and reported as $\log_{10}(\text{titer})$ using the same approach as for the ADA assay (see above).

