9.1.2 NAb (neutralizing antibody)

The NAb assay is based on vWF-platelet interaction. As this assay is not sufficiently drug tolerant to detect NAb under treatment, only pre-dose samples (before first caplacizumab administration, i.e. baseline visit) and wash out samples (FU samples) will be analyzed.

All samples scoring positive in the ADA assay at baseline visit or FU samples will be analyzed in the NAb assay. Samples scoring positive in the NAb assay are titrated. The titer per sample is reported as $\log_{10}(\text{titer})$. Samples scoring negative in the NAb assay will be reported as $<\log_{10}(\text{MRD})$ with $\text{MRD}=2.30$ i.e. $\log_{10}(\text{titer})<0.36$. Positive samples for which no titration can be done due to insufficient sample volume will be reported as $>\log_{10}(\text{MRD})$. These positive samples (for which no titration could be done) should be plotted as $\log(\text{MRD})$ equal to 0.36 in the figure.

Subjects will be classified based on their pre-dose status (i.e. baseline visit) and treatment-emergent (TE) status. Subject classification based on NAb is as follows:

- Pre-dose negative, TE negative: no positive samples
- Pre-dose negative, TE positive: negative baseline visit and one or more positive samples post-dose
- Pre-dose positive, TE negative: positive baseline visit and no titer increase post-dose or all samples scoring negative post-dose
- Pre-dose positive, TE positive: positive baseline visit and titer increase post-dose
- Missing: relevant ADA samples are missing

Subjects with no positive NAb samples will be classified as NAb pre-dose negative, TE negative. In listings, samples not evaluated in the NAb assay will be indicated as not analyzed (NA). In graphical presentations, these samples will be presented as negative results.

Given the possible switch to OL Caplacizumab treatment in case of TTP recurrence, subjects will be classified based on the ADA samples available during the DB period, and the OL period, separately. For the latter subject classification, the Day 1 visit of the OL treatment period will be used as baseline visit. Table 6 below provides an overview of the treatment groups for which the incidence in the different classes of the subject classification based on NAb will be calculated, and the analysis periods for which this will be done.

Table 6: Overview of treatment groups in the subject classification based on NAb

Treatment group	DB period*	OL Caplacizumab period*	Overall study period

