Placebo (no OL Caplacizumab)	X		
Caplacizumab (no OL Caplacizumab)	X		
OL Caplacizumab (after Placebo)		X	

CONFIDENTIAL

OL Caplacizumab (after Caplacizumab)			X
Caplacizumab Total	Combination of 'Caplacizumab (no OL Caplacizumab)' (DB period), 'OL Caplacizumab (after Placebo)' (OL Caplacizumab period), and 'OL Caplacizumab (after Caplacizumab)' (Overall study period)		

* Pre-dose and FU samples only.

9.1.3 Alternative NAb (epitope characterization; null variant assay): ADA with neutralizing potential

To detect ADA with potential neutralizing activity during treatment an alternative NAb assay will be used, consisting of the bridging ADA assay in which an altered caplacizumab molecule (i.e. caplacizumab with mutated complementary determining region [CDR] regions) is added in excess to capture all non-CDR binding ADA. Consequently, using this assay, only ADA binding to the CDRs of the Nanobody are detected. Those ADA are considered to have neutralizing potential, although clinical relevance (i.e., ability to block binding of vWF) will be dependent on affinity and titer level and should be related to PK, PD and efficacy read-outs.

All samples scoring positive in the ADA assay, will be analyzed in alternative nAb assay. Samples scoring positive in the alternative nAb assay are titrated. The titer per sample is reported as $\log_{10}(\text{titer})$. Samples scoring negative in the alternative NAb assay are not titrated and the respective titer is reported as $<\log_{10}(\text{MRD})$ with MRD=96, i.e. $\log_{10}(\text{titer}) < 1.98$.

Subjects will be classified based on their pre-dose status (i.e. baseline visit) and treatment-emergent status. Subject classification based on alternative NAb assay is as follows:

- Pre-dose negative, TE negative: no positive samples
- Pre-dose negative, TE positive: negative baseline visit and one or more positive samples post-dose.
- Pre-dose positive, TE negative: positive baseline visit and no titer increase post-dose or all samples scoring negative post-dose
- Pre-dose positive, TE positive: positive baseline visit and titer increase post-dose
- Inconclusive: no positive samples and drug is present at levels higher than the drug tolerance characteristics of the assay
- Missing: relevant ADA samples are missing

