Subjects with no positive ADA sample will be classified as pre-dose negative, TE negative in the alternative NAb assay. In listings, samples not evaluated in the alternative NAb assay will be indicated as not analyzed (NA). In graphical presentations they will be presented as negative results at the specific sample time points.

Given the possible switch to open-label caplacizumab in case of TTP recurrence, subjects will be classified based on the ADA samples available during the DB period, and the OL period separately. For the latter subject classification, the Day 1 visit of the OL treatment period will be used as baseline visit. Patients who switch to open-label caplacizumab after having received double-blind caplacizumab treatment will be classified based on the DB period and

the overall study period, but not on the OL Caplacizumab period, as the OL Day 1 baseline visit cannot be considered a proper baseline visit for this analysis. Table 7 below provides an overview of the treatment groups for which the incidence in the different classes of the subject classification based on alternative NAb will be calculated, and the analysis periods for which this will be done.

Table 7: Overview of the treatment groups based on alternative NAb

Treatment group	DB period*	OL Caplacizumab period*	Overall study period
Placebo (no OL Caplacizumab)	X		
Caplacizumab (no OL Caplacizumab)	X (i)		
OL Caplacizumab (after Placebo)	X	X (i)	
OL Caplacizumab (after Caplacizumab)	X	Not done	X (i)
Placebo	Combination of 'Placebo (no OL Caplacizumab)' and 'OL Caplacizumab (after Placebo)'		
Caplacizumab	Combination of 'Caplacizumab (no OL Caplacizumab)' and 'OL Caplacizumab (after Caplacizumab)'		
Caplacizumab Total	Combination of 'Caplacizumab (no OL Caplacizumab)' (DB period), 'OL Caplacizumab (after Placebo)' (OL Caplacizumab period), and 'OL Caplacizumab (after Caplacizumab)' (Overall study period), as indicated by (i)		

* FU samples are included in the DB period if the patients are not switching to OL caplacizumab; in the latter case the FU sample is considered part of the OL Caplacizumab period.

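### Treatment-emergent NAb is judged against a baseline sample taken after plasma exchange, which the SAP elsewhere says cannot establish pre-dose antibody status

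*SAP*

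**What the plan says.** **The TE rule.** SAP 9.1.2 classifies each subject by pre-dose status, taken from the baseline visit, and by what follows. TE positive is reached in two ways: "Pre-dose negative, TE positive: negative baseline visit and one or more positive samples post-dose", or "Pre-dose positive, TE positive: positive baseline visit and titer increase post-dose". SAP 9.1.3 uses the same two rules for the alternative (null variant) assay. Neither section sets a minimum titer rise.

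**The samples.** In the NAb assay "only pre-dose samples (before first caplacizumab administration, i.e. baseline visit) and wash out samples (FU samples) will be analyzed", and of these only the ADA-positive ones. Being mADA positive is not a condition.

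**When baseline is drawn.** Protocol 3.2.1 admits a subject who "Requires initiation of daily PE treatment and has received 1 PE treatment" before randomization. Protocol 3.4.11 places Day 1 sampling before the first on-study PE and before the i.v. dose. The double-blind baseline therefore precedes drug but follows one PE.

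**What the SAP says about that sample.** In SAP 9.1.1.1: "No statement will be made on pre-existing antibody (pre-Ab) positivity pre-dose due the plasma exchange (PE) procedure". Two mechanisms are given, transfer of antibody from donor plasma and dilution of the patient's own, and the section notes that "no ADA pre-PE sample will be available to determine the pre-Ab status of the patient". SAP 9.1.1.2 then identifies drug-induced ADA with the mADA assay, which does not detect pre-existing antibody and so needs no baseline.

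**The concern.** The SAP declines to state pre-dose antibody status in one section, then in the next two assigns that status from the same sample and builds a treatment-emergent class on it. The PE caveat is not repeated in 9.1.2 or 9.1.3. The only doubtful class (inconclusive, in 9.1.3) is for drug interference, not for PE.

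Antibody diluted by PE can recover after PE stops, with or without drug, and would then count as TE positive. Donor antibody can do the reverse: it makes baseline positive or raises its titer, so a true response may not register as an increase.

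At stake is a reported safety figure, TE NAb incidence in SAP Tables 14.3.5.4 and 14.3.5.5. The same classes also stratify drug concentration, RICO activity, vWF:Ag and platelet response in Tables 14.3.5.13 to 14.3.5.20. False TE positives there would blur the group in which a real neutralizing effect should show.

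**Working it through.** There is no design figure to reproduce. The check sets the rules against each other and then illustrates how far dilution could reach.

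**1. One subject, two tables.** Suppose pre-existing antibody is diluted below detection at baseline and recovers by follow-up.
- Baseline: ADA negative, so not run in the NAb assay.
- Follow-up: ADA positive, mADA negative, NAb positive.
- SAP 9.1.1.2 class: pre-Ab positive, drug-induced TE ADA negative.
- SAP 9.1.2 class: pre-dose negative, TE positive.

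No rule reconciles the two.

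**2. Interval compared.** Dosing runs 30 days after daily PE, and follow-up visits fall 7 and 28 days after the last dose (Protocol Table 3). For a completer without extension, follow-up samples come about 30 + 7 = 37 and 30 + 28 = 58 days after the last daily PE. They are compared with a sample taken within about a day of an exchange. For early discontinuers the gap can be shorter.

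**3. Cuts.** log10(2.30) = 0.362 for NAb (SAP: 0.36). log10(96) = 1.982 for ADA and alternative NAb (SAP: 1.98). Both agree.

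**4. Dilution, illustrated.** Assumptions, not document figures: one compartment, antibody-free replacement, and V plasma volumes exchanged before randomization. Fraction left = exp(-V). Highest pre-PE titer that reads negative at baseline = cut / exp(-V).

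| V assumed | Fraction left | Fall in log10 titer | NAb titer masked up to (log10) | ADA titer screened out up to |
|---|---|---|---|---|
| 0.5 | 61% | 0.22 | 3.79 (0.58) | 158 |
| 1 | 37% | 0.43 | 6.25 (0.80) | 261 |
| 1.5 | 22% | 0.65 | 10.31 (1.01) | 430 |
| 2 | 14% | 0.87 | 16.99 (1.23) | 709 |

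The last column matters because an ADA-negative baseline sample never reaches the NAb assay. If baseline stays positive, recovery of the same fall meets the any-increase rule, provided it spans at least one step of the dilution series. The SAP does not state that series.

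**5. Donor plasma, same model.** With patient level P and donor level D, the baseline level is P·exp(-V) + D·(1 - exp(-V)). For V = 1 that is 0.368·P + 0.632·D. Baseline is lowered when D is below P and raised when D is above P, whatever the value of V. The documents give neither level, so the net direction is unknown.

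**The case against.** **A reader might infer that PE rebound will be reported as drug-induced neutralizing antibody.** The documents do not support that. Sections 9.1.2 and 9.1.3 and Tables 14.3.5.4 and 14.3.5.5 say TE; drug-induced is kept for the mADA-based classes. Nor is misclassification certain. It needs pre-existing antibody that neutralizes, and further daily PE and mandated corticosteroids act against recovery.

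**A reader might apply the range of 1 to 1.5 plasma volumes to the baseline sample.** The protocol sets that range only from randomization. The earlier PE is at the investigator's discretion and may be smaller or larger.

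**A reader might cite the SAP's remark that** "the OL Day 1 baseline visit cannot be considered a proper baseline visit for this analysis". It stands in the alternative NAb section and concerns subjects already given double-blind caplacizumab, not PE. Open-label Day 1 is sampled before the PE that treats the recurrence.

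**The 9.1.3 assay is less exposed.** It detects only antibody binding the CDRs, so pre-existing antibody directed elsewhere is removed. That stands.

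**Safeguards exist.** Placebo is classified by the same rules (SAP Tables 6 and 7). Listing 16.2.11.1 gives all assay results by time point, and Figure 14.4.1.22 plots them with PE days for each ADA-positive subject. These help, but no summary table joins NAb to mADA. The NAb placebo group in Table 6 also covers only subjects who did not switch.

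**Requiring mADA positivity would be unsafe.** It could drop pre-existing neutralizing antibody boosted by the drug. This is right, and it is why the fix splits rather than filters.

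**Conclusion.** The inconsistency is real and worth correcting. The double-blind TE NAb classes rest on a post-PE sample that SAP 9.1.1.1 treats as unable to show pre-dose status. Applying that statement to NAb is an inference, but a sound one, because only ADA-positive samples enter the NAb assay.

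PE can create or hide TE-positive calls, chiefly at low titers and more plausibly in 9.1.2 than in 9.1.3. Frequency and net direction cannot be derived from the documents. The figures above show only that the mechanism could reach titers a few-fold above the cut, under assumed volumes and ideal washout.

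Immunogenicity is summarized without p-values (SAP 9.2), so the consequence is limited to how a safety incidence is labelled and read.

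**What to change.** In SAP 9.1.2, 9.1.3 and Tables 14.3.5.4 and 14.3.5.5:

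1. For the double-blind baseline, replace the pre-dose labels by *post-PE baseline sample positive* and *post-PE baseline sample negative*.
2. Report TE NAb and TE alternative NAb incidence split by the mADA result of the same post-dose sample. Describe only the mADA-positive part as drug-induced.
3. Keep mADA-negative TE NAb as a separate row, noted as possible PE artefact or boosted pre-existing antibody. Do not drop it.
4. Read both rows against the placebo rate already planned.

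**Cost.** Wording and one derived flag. SAP 9.1.1.2 already sends every ADA-positive sample to the mADA assay, so no new testing is needed.

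**Downsides.** Cells will be small. If the phase II rate of 9% drug-induced TE antibody (Protocol 1.2.5) recurred in 66 caplacizumab subjects (132/2), that is 0.09 × 66, or about 6 subjects with drug-induced ADA, before asking how many are NAb positive. The placebo rate will be imprecise too: with 66 subjects and an assumed rate of 5%, the 95% half-width is 1.96 × √(0.05 × 0.95 / 66) = 5.3 percentage points, and wider once switchers are excluded. Antibody restricted to the C-terminus, which the SAP says mADA may miss, can fall in the mADA-negative row; keeping that row means it is still counted.

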9.2 Analysis

Immunogenicity will be assessed through summary tables and figures, and listing of individual results by subject. Immunogenicity data will be correlated with PK, PD and efficacy endpoints. In addition, immunogenicity will be correlated with possible safety findings. No formal inferential statistics (p-values) will be derived.

All analyses will be run on the safety population, unless specified otherwise.

A detailed list of tables, figures and listings can be found in Section 14.10, Section 15.7 and Section 16.11, respectively.

The immunogenicity results for the pediatric substudy will be reported via listings only.

9.2.1 Subgroup analyses

Analysis of incidence based on ADA/mADA results (overall subject classification) are planned for the following subgroups:

- Hypersensitivity reaction, with categories
 - No hypersensitivity reaction
 - At least 1 hypersensitivity reaction

9.2.2 Exploratory analyses

[REDACTED]

[REDACTED]

[REDACTED]

[REDACTED]

[REDACTED]

[REDACTED]

[REDACTED]

[REDACTED]

10 INTERIM ANALYSES

There are no interim analyses in this study.

11 DSMB REVIEWS FOR SAFETY

A Data Safety Monitoring Board (DSMB) has been appointed by the Sponsor, consisting of an independent group of clinical experts, who are not participating in the study. They are supplemented by an independent statistician. The objective of the DSMB is to review unblinded safety data on SAEs with a focus on mortality rate. The composition, objectives, and role and responsibilities of the independent DSMB are described in a DSMB charter, agreed with the DSMB members and Sponsor. The DSMB charter also defines and document the content of the safety summaries, and general procedures (including communications).

12 CHANGE FROM ANALYSIS PLANNED IN PROTOCOL

12.1 Changes before database lock

No shift tables for Vital signs are produced as they are not representing essential information that is not available elsewhere in the outputs.

In order to reduce any possible bias in the estimation of the effectiveness of Caplacizumab versus Placebo, the main efficacy analysis will be performed on the ITT population instead of

miITT. For the primary endpoint a separate analysis on miITT will be performed as sensitivity analysis.

Per protocol, all samples will be analyzed by a central laboratory, except for pregnancy, screening creatinine and samples of platelet count. However, some extra local laboratory creatinine samples have been analyzed for visits after screening. Those results will only be listed and will not be used for analysis. The extra local creatinine taken for safety reason will not be considered as protocol deviation. Those taken for reasons other than safety will be captured as protocol deviation. The same will apply for the extra PE assessments performed outside of the time point indicated in the schedule of assessment.

12.2 Changes after database lock

Not applicable.

14 INDEX OF TABLES

14.1 General

Table 14.1.1.1: Subject disposition: Tabulation by analysis population

Tabulation of the number of subjects in each of the analysis populations defined in Section 4.1.
Population: all screened population.

Table 14.1.1.2: Subject disposition: Tabulation by country and site

Tabulation of the number of subjects per country and site.
Population: ITT population.

Table 14.1.1.3: Subject disposition: Tabulation by time point

Tabulation of the number of subjects per time point.
Population: ITT population.

Table 14.1.1.4: Subject disposition: First and last contact in the trial

Tabulation of the following 3 dates:

- Date of the first signature on trial ICF or pre-trial ICF
- Last visit date (all visits; including unscheduled visits)
- Last date of contact in the study with any subject (i.e., the last DM.RFENDTC).

Population: all screened population.

Table 14.1.1.5: Subject disposition: Descriptive statistics of the analysis period duration (days)

Descriptive statistics of the analysis period duration. The duration (days) is derived as follows: period end date – period start date + 1. This table will represent phases, periods and subperiods.

Population: ITT population.

Table 14.1.1.6: Trial termination: Tabulation

Tabulation of completion/discontinuations and the reasons for discontinuation.

Population: ITT population.

Table 14.1.1.7: Major protocol deviations: Tabulation

Tabulation of the major protocol deviations per category (DVDECOD) (see Section 5.2 for more details).

Population: ITT population.

Table 14.1.2.1: Demographic data: Tabulation and descriptive statistics

Continuous parameters: descriptive statistics.

Categorical parameters: frequency tabulation.

Population: ITT population.

Table 14.1.2.2: Baseline disease characteristics: Tabulation and descriptive statistics

Continuous parameters: descriptive statistics.

Categorical parameters: frequency tabulation.

Population: ITT population.

Table 14.1.2.3: Concomitant immunosuppressive therapies

Tabulation of type of immunosuppressive therapies (corticosteroid / rituximab / other immunosuppressive).

Population: ITT population.

Table 14.1.2.4: Concomitant immunosuppressive therapies by generic term

Tabulation of the generic terms of immunosuppressive therapies.

Population: ITT population.

Table 14.1.2.5: Concomitant non-immunosuppressive therapies by generic term

Tabulation of the generic terms of non-immunosuppressive therapies.

Population: ITT population.

Table 14.1.2.6: Concomitant antithrombotic therapies by generic term

Tabulation of the generic terms of immunosuppressive therapies.

Population: ITT population.

Table 14.1.2.7: Transfusions

Tabulation of transfusions.

Population: ITT population.

Table 14.1.2.8: Duration of corticosteroids use and cumulative dose of corticosteroids

Tabulation by treatment group during the overall treatment period. Corticosteroids will be reported as prednisolone equivalent dose.

Population: ITT population.

Table 14.1.2.9: Exposure to study medication: Descriptive statistics

Descriptive statistics of treatment duration and compliance, present by sub-period (dPE and post dPE) and overall for the DB treatment period.

Population: safety population.

